¹ ASCVD for this project is defined as history of myocardial infarction, angina, unstable angina, coronary revascularization, percutaneous coronary intervention, transient ischemic attack (TIA) stroke, peripheral artery disease, carotid artery disease ($> 50\%$ luminal obstruction)

² Hypoglycemia for this project is defined as a blood sugar $< 70 \text{ mg/dL}$

Patients recruited into the program will enter either 1) a gradual education period for 2 months followed by pharmacist and navigator-based medication titration, or 2) rapid education in conjunction with pharmacist and navigator-based medication titration via a Collaborative Drug Therapy Management (CDTM) algorithm designed to improve medical therapy for the treatment of type 2 diabetes with cardiorenal comorbidities. The CDTM will be approved by the BWH Pharmacy and Therapeutics committee. We will use A/B testing to optimize the timing of the educational program. Outcomes will include percentage of patients prescribed SGLT2i or GLP1-RA, percentage of prescriptions filled, HbA1c, change in the diabetes treatment satisfaction questionnaire short (DTSQs) score, and Patient Activation Measure (PAM) at enrollment and completion of the program.

Participants whose HbA1c rises to 9.0-9.9% following enrollment as part of their program baseline labs will automatically be assigned to immediate pharmacist and navigator-based medical titration and rapid education. As a result, participants with baseline HbA1c between 9.0-9.9% will remain in the program but will not be part of the A/B testing.

We will generate prototype software to guide DM medication changes based on patient-specific information and to longitudinally monitor each participant's progress through the algorithm and document

clinical and laboratory information. Basic patient demographic, laboratory, medication, and medical history data will be housed in a secure platform database for clinical management and communication.

Briefly describe study procedures. Include any local site restrictions, for example, “Subjects enrolled at Partners will not participate in the pharmacokinetic portion of the study.” Describe study endpoints.

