Potential participants will be screened for eligibility through CardioCompass – an application housing medical data currently in use at DCT – as well as the EHR as described in protocol 2020E000255. If eligible, the patients will be contacted by navigators trained to describe the study procedures, who will ask them whether they would be willing to participate.

Participants who agree to participate will enter either early pharmacist and navigator-led medical titration and concurrent education, or a gradual titration, through which patients will undergo 2 months of diabetes self-management education followed by pharmacist and navigator-led program of medication optimization. Navigators will contact the patient at regular intervals and monitor symptoms and laboratory tests will be obtained per protocol to ensure safety of the prescribed medications. Any symptoms will be evaluated by the program nurse practitioner or physician and managed per standard of care.

The education program for all patients will follow standard diabetes self-management education curricula, focusing on medication adherence, the role and benefit of medical therapy for the treatment of type 2 diabetes, and other self-management behaviors. We will offer written materials of current guideline recommendations and an online web portal with short educational videos about diabetes, cardiovascular risk, and lifestyle and medical interventions. Educational videos produced by study staff will be made available to participants through the Mytonomy (www.mytonomy.com) web-based portal. In addition, materials from <https://knowdiabetesbyheart.org/> – a collaboration between the American Heart Association and the American Diabetes Association – will be shared with patients virtually. We will also offer live webinar, question/answer sessions for patients and providers to gain education and ask questions regarding the medications and program.

Once each participant has been followed for six months, the intervention will conclude with formal written handoff to the patient’s primary care provider (PCP), and the ongoing monitoring of labs, disease management, health care utilization, health outcomes, and medications will continue beyond the program period as per the patient’s PCP.

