Roughly 50% of patients enrolled into this quality improvement program will be allocated into an “education first” pathway, which will provide 4 weeks of digital, paper, and customized video resources to explain the medical rationale and anticipatory guidance regarding diabetes care and therapeutics with proven benefit prior to becoming eligible for medical therapy prescription. In addition to looking at uptake and adherence, we will be measuring baseline and end-of-study Patient Activation Measures for each participant. Patient Activation Measures have been shown to correlate with increased self-care behaviors, medication adherence, and diabetes monitoring (11).

Primary Aim

The primary objective of this study is to create a remote diabetes management platform that compared to baseline, will improve initiation and adherence to contemporary guidelines regarding the use of glucose-lowering medications with cardiovascular and renal benefit for patients with type 2 diabetes and high cardiovascular and/or renal risk.

Secondary Aim(s)

- Evaluate optimal timing of patient education within the program. (measured as prescriptions by randomization arm, prescriptions at 2 months, and patients on therapy at end of study)
- Increase patient disease knowledge, activation, and engagement (as measured with short-form Patient Activation Measure)

Exploratory Aim(s)

Weight and HbA1c

We will compare age, socioeconomic demographics (where available), baseline characteristics and medical history, HbA1c, and demonstrate that they are evenly distributed in the population and between groups. We will report subgroup-specific rates if there are significant differences (e.g., evidence of heterogeneity).

Data Sources

Data will be collected from the electronic health record (HER) and directly from patients. All data will be stored in an encrypted, secure database within the Mass General Brigham firewall and using HIPAA-compliant applications.

Study Sample Size

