For our primary outcome, the percent of patients on either an SGLT2i or GLP-1 RA from baseline to conclusion of the study at 6 months post-enrolment, we will perform a Chi-Square test to determine a difference in the terminal rates at the end of the study to determine treatment effects between groups.

We will develop a cumulative incidence curve displaying patients both prescribed and taking DRIVE medications for the duration of the program.

We will perform t-tests and Fisher's exact test for the baseline univariate analysis. As we will be utilizing A/B allocation there should be no bias or confounding at baseline, however if any significant differences are found, we will correct for these utilizing logistic regression. A/B allocation with 200 patients should cause any confounders to balance between the groups. We will also perform a longitudinal model for binary outcome at 6 months. For our co-secondary outcomes, the change in the HbA1c, and PAM from baseline to the end of the 6-month study, these will be analysed with a paired t-test and we will report a mean and standard deviation. A secondary analysis will be to conduct linear regression models with two variables (baseline HbA1c and baseline weight) to control for any confounders.

We will conduct our analysis via the intention-to-treat principle with two-sided type I error with an alpha of 0.05. For participants with missing outcome data, we will perform a sensitivity analysis with missing outcomes excluded or included as an event.

A priori sub-analyses will be performed based on zip code, baseline HbA1c, race, insurance status, and sex with a p-value threshold of 0.1 for these secondary analyses and we will account for multiple testing. A cox proportional hazards model will be performed to assess time-to-prescription between groups.

After the final data was reviewed, a series of subsequent hypotheses were identified for additional analysis. These analyses are, by definition, post hoc and, therefore, considered hypothesis-generating. A p-value of 0.05 will be considered significant without any correction for multiple comparisons.

Interim Analysis

N/A

Quality Control

Data will be collected from our EHR, the MGB Electronic Data Warehouse (EDW), and patients. Clinical laboratories within MGB system have laboratory certificates available upon request.

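### The Cox model and the 2-month prescribing measure compare an arm held back from prescription with one that is not, and the two documents disagree on how long the hold lasts

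*SAP*

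**What the plan says.** The protocol's Research Design and Methods section gives one arm "a gradual education period for 2 months followed by pharmacist and navigator-based medication titration". Its description of study procedures repeats that "patients will undergo 2 months of diabetes self-management education followed by pharmacist and navigator-led program of medication optimization". The other arm receives rapid education alongside titration from the start.

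The SAP (Research Question and Objectives) allocates about half the patients to an education-first pathway "which will provide 4 weeks of digital, paper, and customized video resources", all of this "prior to becoming eligible for medical therapy prescription". The SAP names the protocol of November 9, 2021 as the latest version. That is the version that says 2 months, so no later protocol explains the change.

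Under Secondary Aim(s), the timing aim is "measured as prescriptions by randomization arm, prescriptions at 2 months, and patients on therapy at end of study". Statistical Methods adds: "A cox proportional hazards model will be performed to assess time-to-prescription between groups". It gives no time origin, no handling of the ineligible period, no check of proportional hazards and no fallback. The primary outcome is counted at 6 months post-enrolment, so enrolment is the natural reading of the origin. The power statement for the A/B comparison uses yet another time point, 3 months.

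**The concern.** Education-first patients cannot receive a programme prescription during the education period, while the other arm can. If education has no effect, the hazard ratio is near 0 during the bar and 1 after it. A Cox model from enrolment averages these into one number, and the average shifts with the length of follow-up.

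The 2-month measure makes no hazard assumption, but it meets the same inequality of access. Under the protocol's period, education-first patients have had no programme prescribing by 2 months. Under the SAP's period they have had about half the window.

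Aim 3 of the protocol is to find the best timing of education. A significant result from either analysis could be read as evidence that timing changes uptake among patients who are offered treatment, when it may show only that one arm was offered treatment later. Because the length of the bar is the experimental variable, the conflict between 2 months and 4 weeks also leaves unclear which delay is being tested.

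**Working it through.** **The plan's own figure.** The SAP gives no calculation for the Cox model or the 2-month measure. Its sample size is 5% v 20%, two-sided alpha 0.05, 100 per arm, 25% dropout, power above 80%. With the pooled formula, n = [1.96·√(2·0.125·0.875) + 0.842·√(0.05·0.95 + 0.20·0.80)]² / 0.15² ≈ 75.1, so 76 per arm, and 76/0.75 = 102 against 100 stated. Power at 75 per arm is 79.9% (pooled) or 81.4% (unpooled). The figure reproduces closely enough to use its inputs.

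**Inputs.** From the documents: 100 per arm; 6 months of follow-up; 20% prescribed at 6 months under navigator titration; a bar of 2 months (protocol) or 4 weeks (SAP). Assumptions: a constant prescribing hazard once eligible, the same in both arms (no effect of education), and no prescribing during the bar.

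**Expected 2-month rates.** r = −ln(1 − 0.20)/6 = 0.0372 per month.
- Immediate titration: 1 − exp(−2r) = 7.2%.
- Education first, 2-month bar: 0%.
- Education first, 4-week bar (28/30.4375 = 0.92 months): 1 − exp(−1.08r) = 3.9%.

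**Direct check of one result.** With 100 per arm and none in the education-first arm, an uncorrected chi-square reaches p<0.05 at 4 v 0 (z = 0.04/√(0.02·0.98·0.02) = 2.02) but not at 3 v 0 (z = 1.75). The chance of 4 or more among 100 at 7.2% is about 93%, which matches the simulation below.

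**Simulation.** 2,000 trials per setting, 20% rate, 100 per arm, no education effect. Ranges are the spread over repeated runs.

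| Quantity | 2-month bar | 4-week bar |
|---|---|---|
| 2-month prescribing, immediate v education first | 7.2% v 0% | 7.2% v 3.9% |
| 2-month chi-square rejects | 93% | 16% |
| Median Cox hazard ratio from enrolment, education first v immediate | 0.65 | 0.83 |
| Cox from enrolment rejects | 22–25% | 8–9% |
| 6-month chi-square rejects | 20–23% | 8% |
| Restricted mean time from enrolment rejects | 51–52% | 14–15% |
| Cox from eligibility, equal windows, rejects | 5% | 4% |

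**Dependence on follow-up.** With an assumed 40% uptake and a 2-month bar, the hazard ratio for immediate v education first is 3.1, 1.6 or 1.3 when follow-up is 3, 6 or 12 months. Only 6 months is planned; the other two show the instability.

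**Sensitivity.**
- 75 per arm: Cox 19% (2-month bar) or 7% (4-week bar); 2-month test 80% or 14%.
- Outside prescribing during the bar at the SAP's secular 5% per 6 months, 100 per arm: Cox 15% or 7%; 2-month test 45% or 11%.
- Uptake of 60% (an assumption), 100 per arm: Cox 78–80% or 25–27%; 2-month test 100% or about 50–52%.
- Clock from eligibility with equal windows: 4.3% to 6.0% across all settings.

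**The case against.** The arms are whole strategies, and the delay belongs to one of them. The programme exists to overcome therapeutic inertia. If education first postpones prescribing without raising uptake, immediate titration really is better on time to prescription. On that view the rejection rates above are detections of a true difference, and the documents nowhere define willingness to start once eligible as the target. This stands as far as it goes: time from enrolment is a fair description of the two strategies. It does not answer whether the timing of education alters uptake among patients who can be prescribed, which is how a result under the timing aim is likely to be read.

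Other limits also stand:
- The Cox model is one sentence among supporting analyses. The primary test is the 6-month chi-square, and the planned cumulative incidence curve would show the delay.
- The SAP lists prescriptions at 2 months as a measure but names no test for it, so reporting it descriptively may change little.
- At the SAP's own 4 weeks and 20% rate, Cox rejection is only slightly above 5%.

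A reader might infer that the 2-month difference is guaranteed. The documents do not support that. Under 4 weeks the education-first arm has had part of the window, and nothing stops outside clinicians from prescribing, so the early hazard may be low rather than zero. A reader might also infer that restricted mean time or the 6-month difference removes the delay. Neither does: from enrolment, restricted mean time rejects more often than Cox.

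**Conclusion.** The point holds for secondary analyses of a stated aim. The hazard ratio from enrolment is low during the bar and changes when it lifts, so the single Cox estimate has no fixed meaning. The 2-month measure reflects almost only the delay under the protocol's bar and mixes delay with any education effect under the SAP's. The conflict between 2 months and 4 weeks is plain in the text and needs no simulation.

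The size depends on which duration applies. At the SAP's 20% rate with 100 per arm and no education effect, it is 22–25% v 8–9% for Cox and 93% v 16% at 2 months. These figures rest on a constant hazard once eligible and no prescribing during the bar. Outside prescribing lowers them, and uptake above 20% raises them.

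It would go too far to call an advantage for immediate titration spurious, since it may be a true strategy effect. Nor does this show the primary analysis to be invalid: the 6-month chi-square carries some of the delay, but it is a legitimate comparison of the strategies at 6 months.

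**What to change.** 1. State one education-first duration in both documents, and say how it relates to the 2-, 3- and 6-month time points.
2. To test the effect of education timing on uptake, compare the arms over equal windows from the date each becomes eligible: enrolment for immediate titration, the end of the fixed education period for education first. The window is 6 − 2 = 4 months or about 6 − 0.92 = 5.1 months. Keep all allocated patients in the denominator, and state how a prescription from an outside clinician during the education period is counted.
3. Replace the single Cox hazard ratio from enrolment with the 6-month difference in cumulative incidence and the difference in restricted mean time to prescription, with 95% confidence intervals. Label both as whole-strategy effects that include the delay, not as a correction for it.
4. Report the 2-month rates descriptively.

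The cost is SAP wording and standard software, with no new data. The single hazard ratio is lost, and the eligibility-based window is shorter than 6 months. The SAP is dated November 16, 2023 and refers to a review of the final data, so an eligibility-based comparison added now should be labelled as added after that review.
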